**Table 2: Imputation Methods for Weekly Average of the Daily Average NRS Pain Scores**

Double-blind Treatment	Reason	Efficacy Analysis	
		Sensitivity 1	Sensitivity 2
Placebo	Discontinued due to AE or Lack of Efficacy	Multiple imputation	Baseline (BOCF)
	Discontinued due to all other reasons	Multiple imputation	Multiple imputation
	Completed study but took excessive rescue medication before week 4 visit	Multiple imputation	Multiple imputation
TV-45070	Discontinued due to any AE or Lack of Efficacy	Multiple imputation with treatment code set to placebo	Baseline (BOCF)
	Discontinued due to other reasons	Multiple imputation	Multiple imputation
	Completed study but took excessive rescue medication before week 4 visit	Multiple imputation	Multiple imputation

### 6.3. Secondary Efficacy Variables and Analysis

#### 6.3.1. Variable Definition

- Weekly average of the average pain score recorded in the evening.
- Weekly average of the average pain score recorded in the morning.
- Weekly average of the worst pain score recorded in the evening (worst pain is defined as the patient-reported worst pain intensity over the prior 24 hours).
- $\geq 30\%$  improvement from baseline in the weekly average of the daily average NRS scores, where improvement from baseline is defined as  $100*(\text{weekly average of the daily average NRS scores at week 4} - \text{baseline weekly average of daily average NRS scores}) / \text{baseline weekly average of daily average NRS scores}$ .
- $\geq 50\%$  improvement from baseline in the weekly average of the daily average NRS scores, where improvement from baseline is defined as  $100*(\text{weekly average of the daily average NRS scores at week 4} - \text{baseline weekly average of daily average NRS scores}) / \text{baseline weekly average of daily average NRS scores}$ .
- NPSI is a patient-reported questionnaire to evaluate the severity of different symptoms of neuropathic pain. The questionnaire contains 10 descriptors and 2 temporal items. Descriptors are scored from 0 to 10, where 0 represents no pain and 10 represents worst pain imaginable. The total score is the sum of the scores of the 10 descriptors (Bouhassira, Attal, Fermanian, Alchaar, et al, 2004). The total score ranges from 0 to 100, where higher scores represent worse pain. If the score for one question is missing the total score will be computed as 10 times sum of scores of 9 descriptors divided by 9. If more than one question is missing then the total score will

be missing. The 2 temporal items will be summarized as continuous variable using descriptive statistics.

- NePQoL is a questionnaire that contains 41 items to evaluate quality of life in patients with neuropathic pain. Each question has responses ranging from strongly agree or always to strongly disagree or never. Questions are scored on a 5-point scale from 1 to 5, where higher scores represent greater pain-related interference in the quality of life (four items will have scores inverted so that higher scores reflect greater pain. “I involve myself with people I am close to as much as I used to despite the pain”, “I can distract myself from the pain”, “I can cope with the pain”, and “I still enjoy my hobbies/leisure activities despite the pain.”). The total score is calculated as the sum of the scores for the individual questions (Poole and Nurmikko 2009). If scores for up to 4 questions are missing then the total score will be computed as 41 times sum of non-missing scores divided by the number of non-missing questions. If responses for more than 4 questions are missing then the total score will be considered missing.
- PGIC is a standardized self-report tool that measures the change in a patient's overall status rating since the start of treatment (Hurst and Bolton 2004) on 7-point scale. The 7-point scale is defined as: 1=very much improved, 2=much improved, 3=minimally improved, 4=no change, 5=minimally worse, 6=much worse, 7=very much worse.
- DSIS is an 11-point scale that asks the patient to “select the number that best describes how much your pain has interfered with your sleep during the past 24 hours.” Response options range from 0 (Did not interfere with sleep) to 10 (Completely interfered with sleep/unable to sleep due to pain).
- First time to reach  $\geq 30\%$  sustained improvement from baseline in the weekly average of the daily average NRS scores will be computed in days from the date of first dose, where the date of first dose is day 1. Those who do not achieve  $\geq 30\%$  sustained improvement from baseline will be censored at date of last dose of study medication. Sustained improvement is defined as an improvement of  $\geq 30\%$  that is maintained until the end of the treatment period.
- Maximal intensity of patients' brush-evoked allodynia, as measured on the 11-point NRS.
- Maximal intensity of patients' punctate-evoked hyperalgesia, as measured on the 11-point NRS using a Medipin.

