4. SELECTION AND WITHDRAWAL OF PATIENTS

4.1. Patient Inclusion Criteria

Patients may be included in the study only if they meet all of the following criteria:

- a. **[Revision 1]** Patient has chronic PHN, defined as pain present for more than 6 months and less than 10 years after onset of herpes zoster skin rash affecting a single dermatome. Patients with more than 1 involved dermatome may also be included, provided the affected dermatomes are contiguous. Patients excluded under this criterion before implementation of Amendment 03 may be rescreened to determine eligibility under the revised criterion.
- b. Patient has average daily pain of at least 4 on the 11-point NRS at screening and during the baseline pain assessment interval (days -7 to -1) immediately before randomization.
- c. Patient must properly assess and record pain intensity in an eDiary for at least 5 of the 7 daily morning measurements and at least 5 of the 7 daily evening measurements during the 7 days immediately before randomization.
- d. **[Revision 1]** Patient is ≥ 18 years of age, with a body mass index (BMI) between 18 and 34 kg/m^2 , inclusive, at screening visit.
- e. If the patient is a woman:
 - The patient cannot become pregnant because she is surgically sterile (hysterectomy or tubal ligation) or postmenopausal for at least 6 months.
OR
 - If fertile, the patient is not pregnant and has negative pregnancy tests at both the screening and randomization visits and agrees to use an acceptable method of contraception (ie, oral contraceptives, hormone implant, intrauterine device, spermicide with barrier method, surgically sterile male sexual partner[s], or no sexual partners) for the duration of the study, including follow-up.
- f. If the patient is a man:
 - The patient is surgically sterile.
OR
 - If capable of producing offspring, the patient must agree to use a barrier method of contraception in combination with a spermicide with any female partner, unless the partner cannot become pregnant because she is surgically sterile (hysterectomy or tubal ligation), she has been postmenopausal for at least 6 months, or she is fertile but using an acceptable method of contraception (ie, oral contraceptives, hormone implant, or intrauterine device) for the duration of the study, including follow-up.

- g. Patient must sign the written ICF for the study and be willing to comply with all study procedures and restrictions.

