4.2. Patient Exclusion Criteria

Patients will be excluded from participating in this study if they meet 1 or more of the following criteria:

- a. Patient has any other severe pain that might confound assessment or self-evaluation of pain due to PHN.
- b. Patient has PHN affecting the face (trigeminal nerve distribution).
- c. **[Revision 1]** Patient has a history, in the judgment of the investigator, of inadequate response to more than 3 adequate courses of treatment with other medications used to treat neuropathic pain (eg, tricyclic antidepressants, serotonin-norepinephrine reuptake inhibitors, anticonvulsants, topical lidocaine, and/or topical capsaicin). Patients excluded under this criterion before implementation of Amendment 03 may be rescreened to determine eligibility under the revised criterion.
- d. Patient is taking oral analgesics (either opioid or non-opioid) or is receiving topical therapy such as the 5% topical lidocaine patch for the treatment of pain and is unwilling or unable to complete a washout period during which the patient will discontinue analgesic therapy or topical pain therapy.
- e. Patient has been treated with topical capsaicin at any time in the past 6 months for neuropathic pain.
- f. Patient has an NRS score of 10 on 1 or more occasions during the baseline pain assessment interval (days –7 to –1) immediately before randomization or NRS scores of 9 on 3 or more occasions during the same time frame
- g. Patient used rescue medication during the 7-day baseline period
- h. Patient has a history of fibromyalgia.
- i. Patient has uncontrolled cardiac, renal, hepatic, or other systemic disorders that, in the opinion of the investigator, may jeopardize the patient.
- j. Patient uses Class Ic anti-arrhythmic drugs such as flecainide or propafenone.
- k. Patient has a resting heart rate <45 or >100 beats per minute (bpm), QRS \geq 120 milliseconds (including complete left and/or right bundle branch block), QT interval corrected for heart rate by Fridericia's formula (QTcF) \leq 320 milliseconds or \geq 470 milliseconds, and, for patients in sinus rhythm, PR <120 milliseconds or \geq 220 milliseconds. (These numerical exclusion criteria will be applied using the mean values of 3 ECGs.)
- l. Patient has second- or third-degree atrioventricular block unless treated with a permanent pacemaker.

- m. Patient has uncontrolled atrial fibrillation or flutter (ventricular rate >100 bpm).

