7.1. Adverse Events

7.1.1. Definition of an Adverse Event

An adverse event is any untoward medical occurrence in a patient administered a pharmaceutical product, regardless of whether it has a causal relationship with this treatment.

In this study, any adverse event occurring after the clinical study patient has signed the ICF should be recorded and reported as an adverse event. Any adverse event occurring after the first application of study drug is considered a treatment-emergent adverse event.

An adverse event can, therefore, be any unfavorable and unintended physical sign, symptom, or laboratory parameter that develops or worsens in severity during the course of the study, or significant worsening of the disease under study or of any concurrent disease, whether or not considered related to the study drug. A new condition or the worsening of a pre-existing condition will be considered an adverse event. Stable chronic conditions (such as arthritis) that are present before study entry and do not worsen during the study will not be considered adverse events.

Worsening of the disease under study will be measured by increased PHN pain scores. Worsening of PHN should be recorded as an adverse event only if the presentation and/or outcome is more severe than would normally be expected from the normal course of the disease in a particular patient.

Accordingly, an adverse event can include any of the following:

- Intercurrent illnesses.
- Physical injuries.
- Events possibly related to concomitant medication.
- Significant worsening (change in nature, severity, or frequency) of the disease under study or other pre-existing conditions. Note: A condition recorded as pre-existing that is intermittently symptomatic (eg, headache) and that occurs during the study should be recorded as an adverse event.
- Drug interactions.
- Events occurring during diagnostic procedures or during any washout phase of the study.
- Laboratory or diagnostic test abnormalities that result in the withdrawal of the patient from the study, are associated with clinical signs and symptoms or a serious adverse event, or require medical treatment or further diagnostic work-up, or are considered

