### 6.2. Primary Efficacy Variable and Analysis

#### 6.2.1. Variable Definition

The NRS is a widely-used, standard one-dimensional scale from 0 to 10 for patient self-reporting of pain. The daily average NRS scores are the average of the 2 NRS scores (recorded in the morning and in the evening) of average pain, defined as the patient-reported average pain intensity over the prior 12 hours. At least 1 of the 2 daily scores must be recorded (non-missing) or the daily average will be considered missing. The daily average NRS scores are the average of evening NRS score on day x and morning NRS score on day x+1. For example, the daily average NRS score on day 1 (day of first study medication) is the average of evening NRS score on day 1 and morning NRS score on day 2. Similarly the daily average NRS score on day 28 is the average of evening NRS score on day 28 and morning NRS score on day 29. The weekly average of the daily average is computed over the 7 days. Baseline is computed using days -7 to -1, week 1 using days 1 to 7, week 2 using days 8 to 14, week 3 using days 15 to 21 and week 4 using days 22 to 28.

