The output data set MI\_OUT, from the above MI procedure, will contain 5 complete data sets with the missing data points filled using the specified imputation methods, and 1 additional variable, \_IMPUTATION\_, to indicate the order of the imputed data sets. Then within each data set, the primary variable, change from baseline at week 4, will be derived by subtracting baseline from week 4. Each data set will be analyzed using the ANCOVA model with the primary variable and the dependent variables, the screening and baseline scores as covariates, pooled study center, treatment and genotype as factors in the model. The following SAS code may be used to analyze the imputed data sets.

```
ODS output diffss=mixed_out;
Proc mixed data=mi_out method=reml;
  By _imputation_;
  Class center armcd genotype;
  Model change4 = center armcd genotype baseline screening;
  Lsmeans armcd/diff;
Run;
```

ARMCD represents the treatment the patient was randomized to receive.

- Step 4: calculate overall p-value and construct 95% confidence interval for the treatment difference.

The output data from the above SAS code will contain the estimate of the mean difference and the standard error of the estimate from each of the 5 data sets. The SAS procedure mianalyze (PROC MIANALYZE) will be used to generate an overall p-value and 95% confidence interval for the treatment difference. The following SAS code may be used.

```
ODS output parameterestimates=parmest;
Proc mianalyze data=mixed_out alpha=0.05 theta0=0;
  Model effects estimate;
  Stderr stderr;
Run;
```

The second sensitivity analysis will be similar to the first one except that the baseline observation carried forward (BOCF) method will be used to impute the missing week 4 weekly average of the daily average NRS pain scores for those who discontinued the study early due to adverse event or lack of efficacy. Details for the week 4 imputation methods for missing weekly average of the daily average NRS pain scores for the two sensitivity analyses are given in [Table 2](#) below.

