### 6.3.2. Secondary Efficacy Analysis

The above secondary efficacy variables will be analyzed in the similar way as the primary analysis for the primary efficacy variable.

- Change from baseline to weeks 1, 2, 3 and 4 in the weekly average of the average pain score recorded in the evening
- Change from baseline to weeks 1, 2, 3 and 4 in the weekly average of the average pain score recorded in the morning

- Change from baseline to weeks 1, 2, 3 and 4 in the weekly average of the worst pain score recorded in the evening (worst pain is defined as the patient-reported worst pain intensity over the prior 24 hours)
- Change from baseline (randomization visit) to weeks 2 and 4 in the NPSI score
- Change from baseline (randomization visit) in DSIS scores at weeks 2 and 4
- Change from baseline (randomization visit) to weeks 2 and 4 in maximal intensity of patients' brush-evoked allodynia, as measured on the 11-point NRS
- Change from baseline (randomization visit) to weeks 2 and 4 in maximal intensity of patients' punctate-evoked hyperalgesia using a Medipin, as measured on the 11-point NRS

In addition, the following analyses will be done:

[figure not shown]
- Percentage of patients with  $\geq 30\%$  improvement and  $\geq 50\%$  improvement from baseline in the weekly average of the daily average NRS scores at week 4 will be analyzed using logistic regression model with pooled study center, treatment as fixed factors and baseline NRS scores as covariate.
- Time to reach  $\geq 30\%$  sustained improvement from baseline in the weekly average of the daily average NRS scores will be summarized using Kaplan-Meier method.
- Patients' global assessment of treatment, as measured by PGIC scores, at weeks 2 and 4 will be analyzed using a MMRM model similar to the primary efficacy variable with pooled study center, week, treatment, and treatment by week interaction as fixed factors and patient as a random factor. The unstructured covariance matrix for repeated observations within patients will be used.
- Change from baseline (randomization visit) to week 4 in the NePIQoL score will be analyzed using an analysis of covariance (ANCOVA) model with pooled study center, treatment as fixed factors and baseline value as covariate. The missing week 4 values will be imputed using last observation carried forward (LOCF) method.

[figure not shown]
SAS code for ANCOVA model

[figure not shown]
```
Proc mixed data=datain order=data;
  Class center treatment;

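### SAP 6.3.1 gives the improvement formula for the 30% and 50% responder endpoints the wrong sign, so as printed only patients whose pain rises can be responders

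*SAP*

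**What the plan says.** SAP 6.3.1 (Variable Definition, secondary efficacy) has one bullet for the 30% responder endpoint and one for the 50% endpoint. In each, "improvement from baseline is defined as" is followed by the same expression, whose numerator is "100*(\text{weekly average of the daily average NRS scores at week 4} - \text{baseline weekly average of daily average NRS scores" and whose denominator is the baseline weekly average. In plain notation it is 100 × (week 4 − baseline) / baseline, paired with thresholds of at least 30% and at least 50%.

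Four other places fix how this must be read:

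- SAP 6.2.1 describes the NRS as a "standard one-dimensional scale from 0 to 10 for patient self-reporting of pain".
- Protocol 7.1.1 fixes the direction: "Worsening of the disease under study will be measured by increased PHN pain scores".
- SAP 6.2.3 uses the same subtraction for plain change: "change from baseline at week 4, will be derived by subtracting baseline from week 4".
- SAP 6.3.2 states the use: the two responder percentages "will be analyzed using logistic regression model with pooled study center, treatment as fixed factors and baseline NRS scores as covariate".

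The results go to summary tables 15.2.5.1 and 15.2.5.2 and to graphs 17.5.1 and 17.5.2.

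**The concern.** The quantity is named improvement, but the formula is signed so that relief is negative. A positive threshold on it selects patients whose pain has risen by at least 30% or 50%. Code that follows the text would count worsening patients as responders and treat every patient who gets better, including one with complete relief, as a non-responder. Code that does the sensible thing would depart from the prespecified definition.

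The protocol prints no formula to fall back on, and the SAP Preface says the SAP prevails where the two differ. Neither SAP 6.3.2 nor the list of changes in SAP section 10 corrects the sign.

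The endpoint is also one that readers will look for. Protocol 1.3.2.2 reports that the earlier crossover study in this indication showed no difference on its primary endpoint, and the signal it cites is the 50% responder result (26.8% versus 10.7%).

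**Working it through.** The documents give no numerical figure for the responder endpoints, so there is none to reproduce. The sample size in SAP 2.3 concerns the primary endpoint and does not enter here.

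**Inputs.** Let b be the baseline weekly average and w the week 4 weekly average, both on 0 to 10 (SAP 6.2.1). Inclusion criterion b in Protocol 4.1 reads "Patient has average daily pain of at least 4 on the 11-point NRS at screening and during the baseline pain assessment interval", so b is at least 4 and the denominator is positive for every eligible patient.

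**Sign.**
- Printed: P = 100 × (w − b) / b. With b > 0, P > 0 only if w > b.
- Intended: I = 100 × (b − w) / b = −P.

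| b → w | Printed P | Meets 30% / 50% | Intended I | Meets 30% / 50% |
|---|---|---|---|---|
| 6 → 3 | −50 | no / no | +50 | yes / yes |
| 6 → 4.2 | −30 | no / no | +30 | yes / no |
| 4 → 0 | −100 | no / no | +100 | yes / yes |
| 6 → 7.8 | +30 | yes / no | −30 | no / no |
| 6 → 9 | +50 | yes / yes | −50 | no / no |

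**Week 4 score needed.** The printed rule requires w ≥ 1.3b (30%) or w ≥ 1.5b (50%). The intended rule requires w ≤ 0.7b or w ≤ 0.5b.

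| Baseline | Printed 30% / 50% | Intended 30% / 50% |
|---|---|---|
| 4 | ≥ 5.2 / ≥ 6.0 | ≤ 2.8 / ≤ 2.0 |
| 6 | ≥ 7.8 / ≥ 9.0 | ≤ 4.2 / ≤ 3.0 |
| 7 | ≥ 9.1 / 10.5, off the scale | ≤ 4.9 / ≤ 3.5 |
| 8 | 10.4 / 12.0, both off the scale | ≤ 5.6 / ≤ 4.0 |

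**Ceilings.** Since w cannot exceed 10, the printed 50% rule is out of reach above b = 10/1.5 = 6.67, and the printed 30% rule above b = 10/1.3 = 7.69.

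**Are such baselines eligible?** Exclusion criterion f in Protocol 4.2 rules out any score of 10 on days −7 to −1, and "NRS scores of 9 on 3 or more occasions during the same time frame".
- With 14 entries recorded on days −7 to −1, the highest eligible mean is (2 × 9 + 12 × 8)/14 = 114/14 = 8.14.
- SAP 6.2.1 pairs each evening with the next morning. The baseline week then includes the day 1 morning score, which criterion f does not restrict, and the maximum is (2 × 9 + 11 × 8 + 10)/14 = 116/14 = 8.29.

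On either reading both ceilings lie inside the eligible range.

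**Illustration on assumed inputs.** Assume a baseline of 6 and mean changes of −1 on placebo and −2 on active (the plan's 1.0-point difference). Take normal changes with an SD from 1.5 to the plan's 2.35.
- Printed 30% rule, P(change ≥ +1.8): z = 2.8/SD on placebo and 3.8/SD on active. This gives about 3% to 12% on placebo and 1% to 5% on active.
- Intended 30% rule, P(change ≤ −1.8): z = −0.8/SD on placebo and +0.2/SD on active. This gives about 30% to 37% on placebo and 53% to 55% on active.

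Under the printed rule the effective drug would appear to have the lower responder rate.

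**The case against.** The strongest reply is that this is a self-evident slip. The sentence itself names the quantity improvement, the titles of graphs 17.5.1 and 17.5.2 use the same word, and Protocol 1.3.2.2 describes response in the earlier study as a reduction in pain. Only one reading is coherent. A competent programmer would reverse the sign, and a table in which complete relief counts as non-response would be caught on review. These are two of twelve secondary endpoints in a Phase 2 study with no multiplicity adjustment, and Protocol 9.6.1.3 planned only descriptive statistics for them.

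Most of that stands and limits the seriousness. It does not remove the error. The SAP now puts both endpoints into a regression model, and it is the document against which code is written and checked.

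Two narrower points also stand. The top of the eligible baseline range depends on which baseline rule is applied (8.14 or 8.29), although nothing turns on it. And SAP 6.4 and some table and graph titles are withheld from the public text, so one can say only that no visible passage corrects the formula.

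**Conclusion.** The concern holds. The sign is wrong in both bullets. For every eligible patient, only a rise in pain of at least 30% or 50% satisfies the printed rule, and for baselines above 7.69 or 6.67 respectively nothing can. This follows from the printed formula, the direction and range of the scale, and the minimum baseline of 4. It needs no distributional assumption; the responder rates in the illustration do, and they show direction only.

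The reach is confined to the two responder endpoints with their logistic models, tables and graphs. The primary analysis and the sample size are unaffected. No error is claimed for time to sustained 30% improvement, because SAP 6.3.1 prints no formula for it. Since the intent is clear, the practical risk is a programming or checking error, or an awkward correction of a responder definition after results are known. It should be fixed, but it does not threaten the trial.

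**What to change.** Before unblinding, amend both bullets in SAP 6.3.1 in one of two ways:

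- define improvement as 100 × (baseline − week 4) / baseline and keep the thresholds at 30% or more and 50% or more; or
- keep the printed percent change and define response as −30% or lower and −50% or lower.

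Optionally, add a clause that time to sustained 30% improvement applies the same corrected expression week by week, so that the sign error is not carried over if the definition is reused.

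The cost is two formulas and one optional clause. Data collection, the primary analysis and the sample size do not change.

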3.11.3. Procedures During Double-Blind Treatment Period (Day 1 Through Day 29 Visit)

The start of study drug treatment occurs on the randomization visit (visit 3, day 1), as detailed in Section 3.11.2. Study drug treatment continues until the evening of day 28.

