### **4.4. Handling Withdrawals and Missing Data**

Missing onset/stop dates of AEs and prior/concomitant medications will not be imputed, and a conservative approach will be taken when assigning treatment-emergent AEs or concomitant medications.

The daily average NRS score is the average of the 2 NRS scores (recorded in the morning and evening). At least 1 of the 2 NRS scores must be non-missing or the daily average will be considered missing. The weekly average NRS score is the average of the daily average over 7 days.

For NePIQoL and NPSI questionnaires that include multiple items/tests, the measurement value at each timepoint is the sum of responses of all items/tests. If the entire questionnaire is not done at a scheduled time point, it will be considered missing and won't be imputed unless otherwise specified. Missing responses for individual items/tests will be imputed if up to 10% of the total items/tests for that scale are missing (up to 4 missing responses for NePIQoL, and 1 missing

response for NPSI). The imputed total is equal to the number of items in the scale times the sum of the non-missing responses divided by the number of non-missing items. If more than 10% of the responses are missing, then the total will be considered missing.

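### If the treatment period ends at planned day 28, SAP 6.3.1 censors early withdrawals who can no longer be sustained responders, so the Kaplan-Meier curve overstates the sustained-response rate

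*SAP*

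**What the plan says.** SAP 6.3.1 defines the time to a first sustained 30% improvement in the weekly average pain score.

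- **Time scale.** The time "will be computed in days from the date of first dose", with the first dose on day 1.
- **Event.** The improvement must be one "that is maintained until the end of the treatment period".
- **Censoring.** Patients who do not achieve a 30% "sustained improvement from baseline will be censored at date of last dose of study medication".

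SAP 6.3.2 summarises this by Kaplan-Meier and names no test. Table 15.2.10.1 and Graph 17.6 place it in the FAS.

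The SAP does not say what the end of the treatment period means for a patient who stops early. Three passages point to the planned period: SAP 2.1 describes a 4-week treatment period, Protocol 4.4 speaks of patients who fail to complete it, and Protocol 3.11.3 says: "Study drug treatment continues until the evening of day 28".

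On the weekly scores, SAP 4.4 says: "The weekly average NRS score is the average of the daily average over 7 days". SAP 6.2.1 fixes the windows, with "week 3 using days 15 to 21 and week 4 using days 22 to 28". Neither section sets a minimum number of days.

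For the week-4 30% and 50% responders, SAP 6.3.2 says that the percentages "will be analyzed using logistic regression model with pooled study center, treatment as fixed factors and baseline NRS scores as covariate". It gives no rule for a missing week-4 average. For NePIQoL the same section does: "The missing week 4 values will be imputed using last observation carried forward (LOCF) method". SAP 6.2.3 gives multiple imputation and baseline carried forward, but only for the primary endpoint's sensitivity analyses.

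**The concern.** Censoring in Kaplan-Meier says that the patient left the risk set but could still have had the event later. A sustained response is different, because whether it counts depends on what happens at the end of the period. If that end is day 28, a patient who stops on day 10 cannot qualify. Last-dose censoring removes that patient from the denominator as if the outcome were unknown, and the curve rises too far.

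The protocol's endpoint (3.3.2) is time to reach 30% improvement, without the sustained condition, and last-dose censoring is conventional for that. The difficulty comes when the SAP adds the condition and censors at last dose.

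Two things are at stake. First, on the day-28 reading a week-4 30% responder is sustained at least from week 4, so the sustained responders and the week-4 responders are the same patients. The Kaplan-Meier output and responder Table 15.2.5.1 could still show different rates for them. Second, if dropout differs between arms, the distortion differs too.

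The responder models have a related gap. Patients without a week-4 average drop out by default, although SAP 3.3 assigns all efficacy analyses to the FAS. These models will be read closely: the earlier crossover study in postherpetic neuralgia missed its primary endpoint, and its positive signal was a 50% responder rate of 26.8% against 10.7% (Protocol 1.3.2.2). That argument bears on the responder models, not on the Kaplan-Meier summary.

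**Working it through.** **The plan's own figures.** The documents give no sustained-response rate to reproduce. Their sample size does reproduce: with a 1.0-point difference, SD 2.35 and two-sided 5%, the t-based power is 80.2% at 88 per arm, and 88 / (1 − 0.20) = 110. The planned dropout is therefore 22 of 110 per arm.

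**Inputs.** From the documents: 20% dropout, 28 treatment days and four 7-day windows. Assumed: 25% of the FAS have a sustained response, onset is equally likely in each week (0.0625 of the FAS per week), and dropouts are not sustained responders. The SAP does not say whether onset is dated at the start or the end of the week, so both are shown.

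**Formula.** KM(28) is the product over event days of (1 − events / at risk). Events precede censoring on tied days.

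**One case in full.** Onset is dated at week end (days 7, 14, 21, 28). Dropout is uniform over days 2 to 27, so 0.2 / 26 = 0.00769 of the FAS leaves per day.

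| Day | Earlier events | Earlier dropouts | At risk | 1 − 0.0625 / at risk |
|---|---|---|---|---|
| 7 | 0 | 5 × 0.00769 = 0.0385 | 0.9615 | 0.9350 |
| 14 | 0.0625 | 12 × 0.00769 = 0.0923 | 0.8452 | 0.9261 |
| 21 | 0.1250 | 19 × 0.00769 = 0.1462 | 0.7288 | 0.9142 |
| 28 | 0.1875 | 26 × 0.00769 = 0.2000 | 0.6125 | 0.8980 |

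The product is 0.7108, so 1 − KM(28) = 28.9% against a true 25.0%.

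**Other patterns, same 25% rate and 20% dropout.**

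| Dropout days | Onset at week end | Onset at week start |
|---|---|---|
| 2–27 | 28.9% | 27.5% |
| 15–27 | 27.7% | 26.0% |
| 2–13 | 30.5% | 29.3% |

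**Censoring at day 28 instead.** The at-risk fractions are 1, 0.9375, 0.875 and 0.8125. The product telescopes to 0.75, so 1 − KM(28) = 25.0% whatever the dropout pattern.

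**Sensitivity.**

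- Earlier onset (50/30/15/5% over weeks 1 to 4, uniform dropout): 27.5% at week end, 26.2% at week start.
- 10% uniform dropout: 26.8% and 26.1%.
- Patients stopping on days 22–27 allowed to qualify (uniform 20% dropout): 28.7% and 27.5%.
- A separate calculation with 26 events among 110 patients (about 30% of 88 completers) and 22 evenly spread withdrawals gives 27.5% and 26.1% against 26/110 = 23.6%. With completer response varied from 20% to 50% and several onset and dropout patterns, the excess runs from 0 to 9.8 points. It is zero if no withdrawal is censored before a later event.

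**Unequal dropout (assumed 10% versus 30%, uniform, true 25% in both arms).** 26.8% versus 31.6% at week end, 26.1% versus 29.0% at week start. The arm with more dropout looks better.

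**Responder models, observed cases only.** Count dropouts as failures and let the true rate be 25%. At 20% dropout the observed rate is 0.25 / 0.80 = 31.3% if every dropout lacks a week-4 average. If those stopping on days 22–27 keep one, only 20 of the 26 dropout days lose it, and the rate is 0.25 / (1 − 0.2 × 20/26) = 29.5%. At 10% versus 30% dropout the pairs are 27.8% versus 35.7% (odds ratio 1.44) and 27.1% versus 32.5% (odds ratio 1.30).

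**The case against.** **The SAP never equates 1 − KM with the FAS response rate.** This stands. The plan promises only a Kaplan-Meier summary. A reader might infer that the SAP misstates a response rate; it does not. The narrower point remains: on the day-28 reading the curve estimates no well-defined proportion. It cannot be rescued as the rate had everyone stayed. If dropouts would have responded as often as completers, 20.0% of the FAS are events and 25% would have been, while 1 − KM is 20.7% to 24.4%.

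**The reading is not settled.** SAP 7.2 computes duration of treatment from each patient's own first and last dose, and the censoring rule also uses own last dose. If the end of the period means that too, patients who stop while improved become events and the Kaplan-Meier point falls away. A reader might conclude that the rule is wrong as written in every case; the text does not support that. It supports planned day 28 as the better reading and an undefined term.

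**The numbers are assumed.** This also stands. The 25% rate, even onset and the 10% versus 30% contrast have no source in the documents. The 30.5% maximum needs every dropout before day 14. The planned 20% applies to randomised patients, and FAS dropout may be lower. The direction between arms cannot be predicted: in the crossover study, skin-reaction discontinuations were 5 on placebo and 2 on active.

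**Observed cases are a natural default for the responder models.** Partly right. Protocol 9.4 sets observed data for by-visit summaries. It does not address models, and it leaves imputation rules to the SAP, which supplies none here.

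**Conclusion.** The concern holds conditionally. With the end of the treatment period read as planned day 28, last-dose censoring overstates the cumulative sustained-response rate whenever a withdrawal is censored before a later event, which is close to certain at 20% dropout. The illustrated size is 1.0 to 5.5 points on an assumed 25% rate (26.0% to 30.5%), and less with earlier onset or less dropout.

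The responder models share a related weakness, an unstated rule for missing week-4 averages. At 20% dropout this would turn 25% into 29.5% to 31.3%.

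A reader might infer that the trial's treatment comparison is biased. The documents do not support that. Equal dropout with equal response gives no between-arm bias, both endpoints are secondary, the Kaplan-Meier summary is descriptive, and the primary analysis is untouched. The change is worth making because it is cheap and because these outputs could otherwise report different rates for the same responders.

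**What to change.** 1. In SAP 6.3.1, define the end of the treatment period as planned day 28 and censor every FAS patient without the event at day 28. Then 1 − KM at day 28 equals the FAS proportion with sustained response. In the same place, state whether a patient who stops on days 22–27 with a partial week-4 average can qualify, and whether onset is dated at the start or the end of the week.
2. In SAP 6.3.2, count a missing week-4 average as non-response in the 30% and 50% logistic models, with an observed-case analysis as supportive.

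The cost is a few sentences before unblinding, with no new data. The downside is that reported rates may be somewhat lower.
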